**Prior/Concomitant Therapy:**

10. Use of prescription or nonprescription drugs and dietary and herbal supplements within 7 days or 5 half-lives (whichever is longer) prior to the first dose of study intervention. (Refer to [Section 6.8](#) for additional details).
11. Current use of any prohibited concomitant medication(s) or those unwilling/unable to use a permitted concomitant medication(s). Refer to [Section 6.8](#) for additional details.

12. Recent exposure to any live or attenuated live virus vaccines within 6 weeks of Day 1.
  - The use of COVID-19 vaccines are allowed. Any live or live attenuated COVID-19 vaccine will require a 6-week time period before admission to CRU. If the participant receives a COVID-19 vaccine during the study period, this should be recorded as a concomitant medication, and standard AE collection and reporting processes should be followed in the event of any AEs to the vaccination

**Prior/Concurrent Clinical Study Experience:**

13. Previous administration with an investigational drug within 30 days (or as determined by the local requirement. 180 days for biologics) or 5 half-lives preceding the first dose of study intervention used in this study (whichever is longer).
14. Participants that have received PF-06823859 or any other interferon alpha or interferon beta therapy at any time in the past.

**Diagnostic Assessments:**

15. A positive urine drug test.
16. Screening supine BP  $\geq 140$  mm Hg (systolic) or  $\geq 90$  mm Hg (diastolic), following at least 5 minutes of supine rest. If BP is  $\geq 140$  mm Hg (systolic) or  $\geq 90$  mm Hg (diastolic), the BP should be repeated 2 more times and the average of the 3 BP values should be used to determine the participant's eligibility.
17. Screening PR  $> 100$  bpm or  $< 50$  bpm. If the PR is greater than 100 bpm or less than 50 bpm, the PR should be repeated 2 more times and the average of the three pulse rate values should be used to determine the participant's eligibility.
18. Baseline standard 12-lead ECG that demonstrates clinically relevant abnormalities that may affect participant safety or interpretation of study results (eg, baseline QTcF interval  $> 450$  msec, complete LBBB, signs of an acute or indeterminate-age myocardial infarction, ST-T interval changes suggestive of myocardial ischemia, second or third-degree AV block, or serious bradyarrhythmias or tachyarrhythmias). If the baseline uncorrected QT interval is  $> 450$  msec, this interval should be rate-corrected using the Fridericia method and the resulting QTcF should be used for decision making and reporting. If QTcF exceeds 450 msec, or QRS exceeds 120 msec, the ECG should be repeated 2 more times and the average of the 3 QTcF or QRS values should be used to determine the participant's eligibility. Computer-interpreted ECGs should be overread by a physician experienced in reading ECGs before excluding a participant.

19. Participants with **ANY** of the following abnormalities in clinical laboratory tests at screening, as assessed by the study-specific laboratory and confirmed by a single repeat test, if deemed necessary:

- AST **or** ALT level  $\geq 1.5 \times \text{ULN}$ ;
- Total bilirubin level  $\geq 1.5 \times \text{ULN}$ ; participants with a history of Gilbert's syndrome may have direct bilirubin measured and would be eligible for this study provided the direct bilirubin level is  $\leq \text{ULN}$ .
- Hemoglobin level  $\leq 120 \text{ g/L}$  ( $12.0 \text{ g/dL}$ );
- Platelet count  $\leq 150 \times 10^9/\text{L}$  ( $150,000 \text{ cells/mm}^3$ );
- WBC count of  $\leq 3.0 \times 10^9/\text{L}$  ( $3000 \text{ cells/mm}^3$ );
- ANC  $< 1500 \text{ cells/mm}^3$ ;
- ALC  $< 800 \text{ cells/mm}^3$ ;
- eGFR  $< 90 \text{ mL/min/1.73 m}^2$  based on the CKD-EPI 2009 equation;
- In the opinion of the investigator or Pfizer (or designee), have any clinically significant laboratory abnormality that may affect participant's safety or interpretation of study data.

20. A positive COVID-19 test by PCR at screening.

**Other Exclusions:**

21. History of alcohol abuse or binge drinking and/or any other illicit drug use or dependence within 6 months of Screening. Binge drinking is defined as a pattern of 5 (male) and 4 (female) or more alcoholic drinks in about 2 hours. As a general rule, alcohol intake should not exceed 14 units per week (1 unit = 8 ounces [240 mL] beer, 1 ounce [30 mL] of 40% spirit or 3 ounces [90 mL] of wine).
22. Blood donation (excluding plasma donations) of approximately 1 pint (500 mL) or more within 60 days prior to dosing.
23. History of sensitivity to heparin or heparin -induced thrombocytopenia.
24. Pregnant and/or breastfeeding females.
25. Unwilling or unable to comply with the criteria in the [Lifestyle Considerations](#) section of this protocol.

26. Investigator site staff or Pfizer employees directly involved in the conduct of the study, site staff otherwise supervised by the investigator, and their respective family members.

### **5.3. Lifestyle Considerations**

The following guidelines are provided:

#### **5.3.1. Meals and Dietary Restrictions**

- Participants must abstain from all food and drink (except water) at least 4 hours prior to any safety laboratory evaluations.
- While participants are confined, their total daily nutritional composition should be approximately 55% carbohydrate, 30% fat, and 15% protein. The daily caloric intake per participant should not exceed approximately 3200 kcal.

#### **5.3.2. Caffeine, Alcohol, and Tobacco**

- Participants will abstain from caffeine-containing products for 24 hours prior to the start of dosing and during clinical confinement at the CRU.
- Participants will abstain from alcohol for 24 hours prior to admission to the CRU and continue abstaining from alcohol during clinical confinement at the CRU. Participants may undergo an alcohol breath test or blood alcohol test at the discretion of the investigator.
- Participants will abstain from the use of tobacco- or nicotine-containing products for 24 hours prior to dosing and during confinement in the CRU.

#### **5.3.3. Activity**

- Participants will abstain from strenuous exercise (eg, heavy lifting, weight training, calisthenics, aerobics) for at least 48 hours prior to each blood collection for clinical laboratory tests. Walking at a normal pace will be permitted;

#### **5.3.4. Contraception**

The investigator or his or her designee, in consultation with the participant, will confirm that the participant has selected an appropriate method of contraception for the individual participant and his or her partner(s) from the permitted list of contraception methods (see [Appendix 4 Section 10.4.4](#)) and will confirm that the participant has been instructed in its consistent and correct use. At time points indicated in the schedule of activities ([SoA](#)), the investigator or designee will inform the participant of the need to use highly effective contraception consistently and correctly and document the conversation and the participant's affirmation in the participant's chart (participants need to affirm their consistent and correct use of at least 1 of the selected methods of contraception) considering that their risk for pregnancy may have changed since the last visit. In addition, the investigator or designee will

instruct the participant to call immediately if the selected contraception method is discontinued or if pregnancy is known or suspected in the participant or partner.

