### 1.3. Schedule of Activities

The SoA table provides an overview of the protocol visits and procedures. Refer to the [STUDY ASSESSMENTS AND PROCEDURES](#) section of the protocol for detailed information on each procedure and assessment required for compliance with the protocol.

The investigator may schedule visits (unplanned visits) in addition to those listed in the SoA table, in order to conduct evaluations or assessments required to protect the well-being of the participant.

Visit Identifier a Abbreviations used in this table may be found in Appendix 7 .	Screening	CRU Confinement										Follow-Up							ET			
		-28 to -2	-1	1					2	3	4	5	8	15	29	43	57	71		100	127	157
Days Relative to Day 1	-	-	-					-	-	-	-	±1	±1	±1	±3	±3	±3	±3	±3	±3	±3	-
Visit Window (days)	-	-	-					-	-	-	-	±1	±1	±1	±3	±3	±3	±3	±3	±3	±3	-
Hours After Dose			0 b	1	2	6	12	24	48	72	96	-	-	-	-	-	-	-	-	-	-	
Informed consent	X																					
Demography	X																					
CRU confinement		X	→	→	→	→	→	→	→	→	X											
Visit to the CRU	X	X									X	X	X	X	X	X	X	X	X	X	X	
Inclusion/exclusion criteria	X	X																				
Medical/medication history (update)	X	X																				
History of illicit drug, alcohol and tobacco use	X	X																				
Report prior or concomitant treatments	X	X	→	→	→	→	→	→	→	→	X	X	X	X	X	X	X	X	X	X	X	
Contraception check	X	X									X	X	X	X	X	X	X	X	X	X	X	
Physical exam (including height and weight at screening, only) c	X	X																			X	
Single 12-Lead ECG	X	X								X			X		X		X	X	X	X	X	
Supine blood pressure, pulse rate and temperature	X		X							X			X		X		X	X	X	X	X	
Chest radiograph d	X																				X	
Serious and nonserious AE monitoring	X	→	→	→	→	→	→	→	→	→	X	X	X	X	X	X	X	X	X	X	X	
Study intervention administration			X e																			
Safety laboratory (after ≥4-hour fast) including PT, INR, aPTT	X	X						X			X	X	X		X		X	X	X	X	X	
Viral surveillance (CMV, VZV, EBV, HHV6, HSV-1, HSV-2)	X										X		X		X					X	X	

Visit Identifier a Abbreviations used in this table may be found in Appendix 7 .	Screening	CRU Confinement										Follow-Up							ET		
		-28 to -2	-1	1					2	3	4	5	8	15	29	43	57	71		100	127
Days Relative to Day 1	-28 to -2	-1	1					2	3	4	5	8	15	29	43	57	71	100	127	157	-
Visit Window (days)	-	-	-					-	-	-	-	±1	±1	±1	±3	±3	±3	±3	±3	±3	-
Hours After Dose		0 b	1	2	6	12	24	48	72	96	-	-	-	-	-	-	-	-	-	-	

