### 2.3. Benefit/Risk Assessment

A single dose of PF-06823859 is not expected to provide any clinical benefit to healthy participants. This study is designed primarily to generate safety, tolerability, and PK data for further clinical development.

Nonclinical data to date ([Section 2.2](#)) has not identified any risk to reproductive organs in sexually mature cynomolgus monkeys, the pharmacologically relevant species. Given that an ePPND study will be conducted later in development, this protocol that allows enrollment of WOCBP has requirements for pregnancy testing (WOCBP only) and use of contraceptives to mitigate unintended exposures.

There is a theoretical risk that alterations in bone may occur based on published observations of osteopenia in mice genetically deficient in IFN- $\beta$ . The potential for bone effects was assessed in the 3-month GLP toxicity study in sexually mature cynomolgus monkeys, and there were no microscopic findings in bone, nor alterations in circulating bone-related

biomarkers. However, the potential for bone effects in developing/growing bones has not been specifically assessed in growing animals. This risk is considered to be low given the lack of observed effects in the GLP toxicity study as well as the limited duration of total exposure to PF-06823859 in this planned study. While appropriate risk mitigation has been employed, possible risks will be communicated to study participants in the ICD.

There is a potential risk of increased susceptibility to viral infections with IFN- $\beta$  blockade as with any antagonist of Type 1 interferon signaling (eg, anti-IFNAR1, anti-IFN- $\alpha$ , JAK inhibitors). Viral monitoring will be conducted as a precautionary measure to ensure participant safety. Furthermore, during the pandemic, study participants could be infected with the SARS-CoV-2 during study participation. This could lead to increased health risk for this participant and others in the study. Thus, participants must undergo COVID-19 specific assessments according to the [SoA](#).

The clinical impact of these potential risks will be minimized through the proposed standard, intensive, inpatient monitoring of the participants following administration of single, IV dose of the study intervention.

More detailed information about the known and expected benefits and risks and reasonably expected adverse events of PF-06823859 may be found in the IB, which is the SRSD for this study.

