#### 4.2.1. Choice of Contraception/Barrier Requirements

Human reproductive safety data are not available for PF-06823859, but there is no suspicion of human teratogenicity based on the intended pharmacology of the compound. Therefore, the use of a highly effective method of contraception is required (see [Appendix 4](#)).

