### **6.8. Concomitant Therapy**

Use of prescription or nonprescription drugs and dietary and herbal supplements are prohibited within 7 days or 5 half-lives (whichever is longer) prior to the first dose of study intervention. Limited use of nonprescription medications that are not believed to affect participant safety or the overall results of the study may be permitted on a case-by-case basis following approval by the sponsor. Acetaminophen/paracetamol may be used at doses of  $\leq 1$  g/day.

Hormonal contraceptives that meet the requirements of this study are allowed to be used in participants who are WOCBP (see [Appendix 4](#)).

All concomitant treatments taken during the study must be recorded with indication, daily dose, and start and stop dates of administration. All participants will be questioned about concomitant treatment at each clinic visit.

Treatments taken within 28 days before the first dose of study intervention will be documented as a prior treatment. Treatments taken after the first dose of study intervention will be documented as concomitant treatments.

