### 10.4.2. Female Participant Reproductive Inclusion Criteria

A female participant is eligible to participate if she is not pregnant or breastfeeding, and at least 1 of the following conditions applies:

- Is not a WOCBP (see definitions below in [Section 10.4.3](#)).

OR

- Is a WOCBP and using a contraceptive method that is highly effective (with a failure rate of <1% per year), preferably with low user dependency, as described below during the intervention period and for at least 157 days after the last dose of study intervention, which corresponds to the time needed to eliminate any reproductive safety risk of the study intervention(s) (*5 terminal half-lives*). The investigator should evaluate the effectiveness of the contraceptive method in relationship to the first dose of study intervention.
- Is a WOCBP and using a contraceptive method that is highly effective (with a failure rate of <1% per year), with high user dependency, as described below during the intervention period and for at least 157 days after the last dose of study intervention, which corresponds to the time needed to eliminate any reproductive safety risk of the study intervention(s) (*5 terminal half-lives*). In addition, a second effective method of contraception, as described below, must be used. The investigator should evaluate the

effectiveness of the contraceptive method in relationship to the first dose of study intervention.

A WOCBP agrees not to donate eggs (ova, oocytes) for the purpose of reproduction during this period. The investigator should evaluate the effectiveness of the contraceptive method in relationship to the first dose of study intervention.

The investigator is responsible for review of medical history, menstrual history, and recent sexual activity to decrease the risk for inclusion of a woman with an early undetected pregnancy.

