##### **Highly Effective Methods That Have Low User Dependency**

1. Implantable progestogen-only hormone contraception associated with inhibition of ovulation.
2. Intrauterine device.
3. Intrauterine hormone-releasing system.
4. Bilateral tubal occlusion (eg, bilateral tubal ligation).
5. Vasectomized partner.
  - A vasectomized partner is a highly effective contraceptive method provided that the partner is the sole sexual partner of the WOCBP and the absence of sperm has been confirmed. If not, an additional highly effective method of contraception should be used. The spermatogenesis cycle is approximately 90 days.

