##### **Highly Effective Methods That Are User Dependent**

6. Combined (estrogen- and progestogen-containing) hormonal contraception associated with inhibition of ovulation.
  - Oral;
  - Intravaginal;
  - Transdermal;
7. Progestogen-only hormone contraception associated with inhibition of ovulation.
  - Oral;
  - Injectable.
8. Sexual abstinence.

- Sexual abstinence is considered a highly effective method only if defined as refraining from heterosexual intercourse during the entire period of risk associated with the study intervention. The reliability of sexual abstinence needs to be evaluated in relation to the duration of the study and the preferred and usual lifestyle of the participant.

One of the following effective barrier methods must be used in addition to the highly effective methods listed above that are user dependent:

- Male or female condom with or without spermicide;
- Cervical cap, diaphragm, or sponge with spermicide;
- A combination of male condom with either cervical cap, diaphragm, or sponge with spermicide (double-barrier methods).

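### The contraception check in Protocol 5.3.4 asks a woman to affirm only one method where Appendix 4 requires two

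*Protocol*

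**What the plan says.** Inclusion criterion 1 (Protocol 5.1) sends female participants to Section 10.4.2 for the reproductive criteria. For a WOCBP whose highly effective method depends heavily on the user, 10.4.2 adds: "In addition, a second effective method of contraception, as described below, must be used". This applies through at least 157 days after the dose. Section 10.4.4 places combined hormonal contraception (oral, intravaginal, transdermal), progestogen-only contraception (oral, injectable) and abstinence in the user-dependent group, and repeats the rule: "One of the following effective barrier methods must be used in addition to the highly effective methods listed above that are user dependent".

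Methods of low user dependency generally stand alone. The exception in 10.4.4 is a vasectomized partner who is not the only partner, or whose absence of sperm is unconfirmed: "If not, an additional highly effective method of contraception should be used".

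Section 5.3.4 describes what happens at the visits marked for contraception in the Schedule of Activities. The participant is reminded to use highly effective contraception, and the conversation and her affirmation are charted. The content of that affirmation is: "participants need to affirm their consistent and correct use of at least 1 of the selected methods of contraception".

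**The concern.** The charted affirmation is set below the rule it is meant to verify. For a woman on a user-dependent method the rule is two methods, and the affirmation is complete with one. A site that follows 5.3.4 to the letter could record a satisfactory check at every visit and never learn that the barrier had been dropped.

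The case is foreseeable, because Section 6.8 permits the methods concerned: "Hormonal contraceptives that meet the requirements of this study are allowed to be used in participants who are WOCBP". It also bears on participant protection. Section 2.3 explains that WOCBP are enrolled before the enhanced pre- and postnatal development study has been done, and that the protocol therefore has "requirements for pregnancy testing (WOCBP only) and use of contraceptives to mitigate unintended exposures". Section 5.3.4 gives the reason for repeating the check: pregnancy risk may have changed between visits. Finding a lapse is thus its stated purpose. What is at stake is participant safety and internal consistency. No endpoint, analysis set or summary depends on it.

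**Working it through.** The plan gives no figure to reproduce. The check is a comparison of texts and a count of visits.

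**Methods required against methods affirmed**

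| Participant | Required by Appendix 4 | Affirmed under 5.3.4 | Match? |
|---|---|---|---|
| WOCBP, implant, IUD, hormone-releasing system or tubal occlusion | 1 | at least 1 | yes |
| WOCBP, vasectomized partner meeting both conditions | 1 | at least 1 | yes |
| WOCBP, vasectomized partner not meeting them | 2 | at least 1 | no |
| WOCBP, user-dependent hormonal method | 2 (method plus barrier) | at least 1 | no |
| Man | 1 (condom or abstinence, 10.4.1) | at least 1 | yes |

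Abstinence falls under the same two-method wording in 10.4.4. It is left out of the table because an added barrier has little practical role there.

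**Does the rest of 5.3.4 close the gap?** It does not.

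- The selection step and the instruction to call the site both refer to a single method.
- The reminder concerns highly effective contraception. Appendix 4 describes the add-on barriers as effective, not highly effective, so the reminder does not prompt for one.

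**Do controls elsewhere close it?** Only in part.

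- Section 6.8 has participants asked about concomitant treatments at each visit. The record is of indication, daily dose and dates, which would capture a pill but is not designed to capture condom use.
- Pregnancy tests (8.2.9 and the Schedule of Activities) detect a pregnancy after it has happened.

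**How often the check is made.** The "Contraception check" row of the Schedule of Activities, aligned to its visit header, gives:

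- before dosing: screening and Day -1, which is 2;
- after dosing: Days 5, 8, 15, 29, 43, 57, 71, 100, 127 and 157, which is 10;
- total scheduled: 2 + 10 = 12, plus the early termination visit.

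The row for visits to the CRU has the same pattern, which supports the alignment. Participants are confined from Day -1 to Day 5, so a lapse could matter in practice at the 10 - 1 = 9 later checks.

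**How many women.** About 12 participants are planned (4.1, 9.5). The documents give no expected number of WOCBP and no split by method. The number affected therefore lies between 0 and the number of WOCBP enrolled.

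**The case against.** The strongest reply is that nothing has been relaxed. Appendix 4 binds through inclusion criterion 1, it says the second method is mandatory, and 5.3.4 points the investigator to 10.4.4. One method is a minimum, so a site may chart both. All of this is correct. It shows that the requirement is sound; it does not show that the check tests it.

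A second reply is that correct use of the pill, read together with 10.4.4, already includes the barrier, so a woman on the pill alone could not honestly affirm. The wording does not support this. Section 10.4.2 calls the barrier a second method, and 5.3.4 speaks of one among several selected methods. On those terms the pill alone satisfies the sentence.

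A third reply concerns size. Section 4.2.1 reports no suspicion of human teratogenicity from the pharmacology, and Section 2.3 reports no nonclinical risk to reproductive organs. A woman who drops the barrier is still on a method that 10.4.2 classes as failing in under 1% of users per year. Take the extreme case in which all 12 participants are WOCBP on the pill alone for the whole period, with failure at that 1% limit:

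12 × 0.01 × 157/365 = 0.05 expected pregnancies.

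This stands as evidence that the absolute risk is small, and it would scale in proportion if failure in actual use were higher. The protocol nevertheless chose to require a second method, and the check should verify what was chosen.

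Finally, a minimum of one is right for men and for most methods of low user dependency. That also stands, and any rewording must preserve it.

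**Conclusion.** The inconsistency is real and lies in the current text. A WOCBP on a user-dependent hormonal method can satisfy the check in 5.3.4 with one method while breaching the two-method rule in 10.4.2 and 10.4.4. The same holds for a woman relying on a vasectomized partner who does not meet the conditions in 10.4.4. The gap is present at all 10 post-dose checks, 9 of them after discharge.

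The point is minor. The number of women affected is unknown and may be zero, the expected number of resulting pregnancies is small, other controls operate, and no PK or safety analysis changes. The conclusion rests on reading the affirmation as worded; a site that already records both methods would have no gap in practice.

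**What to change.** In 5.3.4, replace the one-method affirmation with affirmation of consistent and correct use of all methods that Appendix 4 requires for that participant:

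- user-dependent method: the method and the barrier;
- method of low user dependency: that method alone;
- vasectomized partner not meeting the conditions in 10.4.4: the additional highly effective method as well;
- men: the requirement in 10.4.1.

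As a small related clarification, Section 4.2.1 says that "the use of a highly effective method of contraception is required" without saying of whom, and the reminder in 5.3.4 does the same. Both could state that this applies to WOCBP and that men follow 10.4.1.

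The cost is one phrase in 5.3.4, a clause in 4.2.1 and a matching change to whatever the site uses to chart the check. No visits, samples or procedures are added. A change this small need not prompt an amendment of its own and can go into the next one. Amendment 1 already edited 10.4.4 as a nonsubstantial change. Until then the sponsor can ask the site to chart both methods, which the present wording allows.
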